## STUDY PROCEDURES

### Experimental protocol

#### Participants

Participants will be patients who have suffered from chronic pain, and undergone insertion of DBS electrodes into various cerebral areas, including the ACC, sensory thalamus and PAG or Spinal Cord Stimulation including targeted stimulation of the Dorsal Root Ganglion (DRG stimulation), or who have been offered noninvasive analgesic stimulation, such as transcutaneous electrical nerve stimulation (TENS) or pulsed shortwave therapy (PSWT).

#### Procedure:

#### Intervention Group:

Pre-operatively and post-operatively (<6 weeks and 6 months), participants will undergo a full Quantitative Sensory Testing (QST) protocol and Autonomic protocol including microneurography. Participants will also undergo EEG/MEG recording and pre-operative MRI at the Oxford Centre for Human Brain Activity (OHBA) if this has not been done prior to recruitment.

During their inpatient stay, participants will perform a distraction mental task four times. Each time they will be in an 'assigned' state, such as 'resting', with therapeutic stimulation (DBS, SCS, DRG, or noninvasive stimulation), with 'medication' or with 'painful stimulation'. Local field potentials are recorded from the electrodes whilst doing the mental task. Cortical activity will also be recorded using EEG. The order of the patients' states will be randomised. Any experiments in the off medication state will be after 24 hours off analgesics such as paracetamol and codeine-based drugs, making sure that the drug effect has vanished.

Participants will also perform a short computer-based task to measure cognitive performance, including attention, working memory and task-switching. Each subtask is less than 5 minutes, and participants will perform no more than 6 such tasks in succession.

#### Control Group:

In the control group, participants will undergo a full Quantitative Sensory Testing (QST) protocol and Autonomic protocol including microneurography. Participants will also undergo MRI, EEG/MEG analysis at the Oxford Centre for Human Brain Activity (OHBA) and TMS/tDCS at the John Radcliffe Hospital.

During EEG/MEG recordings, participants will perform a short computer-based task to measure cognitive performance, including attention, working memory and task-switching. Each subtask is less than 5 minutes, and participants will perform no more than 6 such tasks in succession.

## **MRI**

Once contraindications to magnetic resonance imaging are excluded by use of the facility's screening forms, the risks of undergoing a scan are minimal. A trained scanner operator or radiographer will go through a list of possible risks with the participant before scanning. The MRI scanner consists of a large powerful magnet. Magnetic resonance imaging uses no ionising radiation. There are, however, potential hazards associated with MRI and the scanning of participants including the presence of surgical implants, participants' clothing, jewellery (such as body piercings) bodily habitus, or medical conditions. A comprehensive list of potential risks has been compiled, and the participant should be checked against this by the operator, prior to entering the controlled areas of the MRI scanners. During the actual scanning procedure, the scanner produces loud banging noises and the participant will be given suitable hearing protection (earplugs). There is a small mirror that will allow them to see out of the scanner. During the experiment, the participant will be able to communicate with the operator in the control room. In addition, they will be given a call button, which allows them to alert the operator at any time. People with a history of claustrophobia may be excluded from participation in the study. All participants will still be introduced carefully to the scanner and allowed to leave at any stage, should they wish to do so. Once in the scanner, participants will be able to indicate immediately if they wish the scanning to cease by pressing a call button in their hands

## Rationales behind this protocol

In order to be able to determine whether LFP 'signatures' are related to pain states per se, we need to be able to look at the LFPs during modulation of those pain states. If a particular signature correlates with the degree of pain (measured using a visual analogue score), we can only show cause and effect by either endogenous modulation (distraction mental task) or exogenous modulation (increasing or decreasing the pain using painful stimulation or analgesia respectively). The rationale behind the QST is to precisely define the pain characteristics for each patient. The autonomic parameters need to be tested before the intervention and after acute and chronic stimulation to look at possible plasticity effects

## Microneurography

This technique entails insertion of two very fine needles (microelectrodes, 30-40 microns in diameter, less than the diameter of a human hair) below the knee. The first will record directly from the common peroneal nerve whilst the second will lie subcutaneously as a reference. We will perform this bilaterally. This is an established technique and the only one enabling direct measure of peripheral sympathetic nerve activity. Neurograms will be recorded with stimulation On and then Off during the same sitting. The maximum time the needle will remain within the tissue will be 45 minutes. We will measure galvanic skin response (sweating), continuous non-invasive blood pressure, ECG and tilt table testing during the same sitting. In some patients, we will measure ambulatory blood pressure for 24 hours (whilst at home).

## Quantitative Sensory Testing

A standard battery of tests (e.g. the German Research Network on Neuropathic Pain (DFNS) protocol will be used. This consists of measurements of pain threshold and sensation using heat, pressure, pin prick, vibration, and electrical stimuli. Proprioception will be tested by measurement of tendon reflexes and surface electromyography. We will use a Somedic Sensebox and ThermoTest equipment. QST has been used in a number of studies involving neuromodulation and spinal cord stimulation in particular. The rationale for its use is that we are looking for an 'objective' measure of pain which can be provided by looking at pain thresholds etc. whereas simply monitoring 'visual analogue score' will not validate our cerebral signature as an objective measure as it is subject to reporting bias.

## Magnetoencephalography

This procedure is a non-invasive method of detecting changes in the magnetic fields around the scalp which correspond to underlying neural activity. The protocol would involve recording these signals from both hemispheres of the brain, during “on” and “off” stimulation periods to determine if there is a difference in laterality of brain processing during dorsal root ganglion stimulation. We will simultaneously evaluate the aforementioned vital sign evaluations (ECG, blood pressure) and QST to determine the differences between stimulation-induced brain signals and sensory signals and how they correlate with autonomic nervous system function. For those patients who have not undergone MRI Brain pre-operatively, this will be facilitated at the time of MEG recruitment for purposes of pain signal localization.

## Non-invasive Brain Stimulation

Transcranial Magnetic Stimulation (TMS) and Transcranial Direct Current Stimulation (tDCS) have arisen as novel non-invasive brain stimulation (NIBS) techniques used in experimental and therapeutic applications for a variety of neurologic disorders. Depending on the placement of anode and cathode, they have been found to produce intracortical facilitation and inhibition, which provides a unique opportunity to identify causal relationships between brain region activity and clinical/behavioural effects.

Studies have shown that anodal tDCS to primary motor cortex (M1) and dorsolateral prefrontal cortex (dlPFC) can result in short-term and long-term relief of neuropathic pain [Ngyernam et al, 2013]. Possible mechanisms of this pain relief are posited to occur via restoration of defective intracortical inhibition at M1 in patients suffering from neuropathic pain [Portilla et al, 2013]. The goal of the proposed experiment would be to investigate the effect of intracortical inhibition of the identified MEG pain signals, or, intracortical facilitation of pain relief centres, to validate whether they are representative of pain signalling or a cortical epiphenomenon of neurostimulation. The following treatment groups:

M1 NIBS-SCS/DRG Stim(positive control) vs. MEG signal-targeted NIBS-SCS/DRG Stim vs. sham NIBS-SCS/DRG Stim (negative control)

Would be evaluated before and after 30 minutes of stimulation with Visual Analogue Scale (VAS), Neuropathic Pain Symptom Inventory (NPSI) and EuroQol 5D (EQ-5D) as primary, secondary and tertiary endpoints for evaluation of the effect of cortical facilitation/inhibition on spinal/dorsal root ganglion stimulation. Each participant will undergo a maximum of 5 sessions, each session taking place at least one day apart.

Whereas non-invasive brain stimulation has been used safely in patients with spinal cord stimulators (Schlaier et al., 2007) this technology has not been explored for safety in patients with metallic head/brain implants, and as such, tDCS will not be implemented in patients treated with Deep Brain Stimulation.

The seizure risk from rTMS is usually during low frequency (<0.1%), whereas therapeutic pain relief has been shown with high frequency TMS. Nevertheless, prior to TMS participants will be excluded from participation if they are sleep deprived prior to study, have a family history of seizures, have a significant history of alcohol use or previous neurological condition, factors which may increase the risk of TMS-induced seizure.

### **Distraction mental task**

The task includes 15 sections, including 5 rest, 5 easy and 5 difficult ones. Each section lasts around one minute. The sequence of these sections will be randomised.

In the rest section patients will just need to concentrate on their pain, and after the section patients will choose a score on the visual analogue scale on the screen, indicating how their pain is during the section.

In the easy task section patients will need to remember the colour of the T-shape figure shown on the screen before starting the easy section. When the section begins, the screen will show many T-shape figures, one by one, with various colours. Whenever seeing the correct colour, as shown before the section, patients need to push a button of the computer's keyboard. After the section patients will choose a score on the visual analogue scale, indicating how their pain is during the task section.

In the difficult task section patients will need to remember the colour and the orientation of the T-shape figure shown on the screen before starting of the section. When the section begins, the screen will show many T-shape figures, one by one, with various colours and orientations. Whenever seeing the figure with the correct colour and orientation patients need to push a button of the computer's keyboard. After the section patients will choose a score on the visual analogue scale, indicating how their pain is during the task section.

### **Various patients' states**

#### **State 1 – resting state, without stimulation or drugs**

Participants will do the mental task when their stimulator is off. In addition, they will not take their everyday pain medications for at least 24 hours before the task

**State 2 – Therapeutic stimulation state, with stimulation on**

Participants will do the mental task when their stimulators are on and at the stimulation parameters producing the most pain relief.

**State 3 – medication state, with patients' everyday medications for pain relief**

Participants will do the mental task with their usual pain medications. Their stimulators will be turned off too.

**State 4 – pain stimulation state, with peripheral stimulation to induce patients' pain symptom**

Participants will do the mental task when their stimulator is turned off. We will use peripheral stimulation to induce pain when they are doing the task. This peripheral stimulation will take the form of a Somedic Thermotest or equivalent heat stimulus, an electrical stimulus, or a mechanical stimulus, just above the pre-measured pain threshold.

**Summary of the possible combinations of participants' experimental states and the mental task they are having, and the questions that each combination can address (explained below)**

State Task	Resting	Therapeutic Stim- ulation on	Medication	Pain stimulation
Rest	Rest LFPs	Neuro modulation effect	Drug effects on the target	Effect of painful stimulus on targets
Easy	Endogenous pain modulation	Stim + endogenous pain modulation effect	Drug + endogenous pain modulation effect	Effect of endogenous modulation on pain signatures induced by painful stimulus
Difficult	Endogenous pain modulation	Stim + endogenous pain modulation effect	Drug + endogenous pain modulation effect	Effect of endogenous modulation on pain signatures induced by painful stimulus

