## BACKGROUND AND RATIONALE

We want to know whether there is a brain signature of pain. Pain perception is very subjective, but if we can find a pain signature, we can detect the objective pain feeling of patients, and we can modulate it to relieve patients' chronic pain.

Besides this, we also want to study the endogenous pain modulation pathway. The more we understand it, the more effective pain treatment we can provide. Pain perception can be altered, and abundant evidence has demonstrated that stimulation of the brainstem (ventrolateral column of the PAG) can activate the endogenous pain modulation pathway to inhibit the pain signal input at the level of the spinal cord. Richardson and Akil, and Hosobuchi and colleagues translated this body of knowledge to clinical use and reported pain relief in patients given chronic stimulation of the PAG. Since then, deep brain stimulation (DBS) of the PAG has been successfully carried out all over the world and has been proved as an effective treatment for pain relief in chronic medicine-refractory pain patients.

Even though the aforementioned mechanism is well-studied, it is still unclear whether the PAG may exert its pain-modulation effect by alternative pathways in addition. Animal studies have shown that the PAG has direct projections to the thalamus in many species. Likewise imaging studies in humans have demonstrated direct connections between the PAG and the thalamus. Therefore, it is reasonable to suggest that the PAG may affect the thalamus to modulate pain perception, and the thalamus, traditionally regarded as a sensory relay centre, may also be able to project to the PAG to modulate pain. However, much less attention has been paid to this suggestion.

In this human study, we take advantage of the DBS of various cerebral nuclei related to pain perception, and use a mental task to induce patients' endogenous pain modulation, to determine whether there is cerebral signature of pain, and to test our two hypotheses: 1. that the PAG modulates pain perception not only via its pathway to the spinal cord, but also via more direct ascending connections to the thalamus; 2. that the thalamus can also affect the PAG to modulate pain, rather than being merely a relay centre.

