## Summary of Study Design

Pre-operatively, before 6 weeks post-operatively and at 6 months post-operatively, patients will undergo standard Quantitative Sensory Testing (QST), EEG, MEG, EMG, microneurography and measurement of autonomic parameters (heart rate, 24 hour ambulatory blood pressure, ECG and galvanic skin response). These sessions will not last longer than 2 hours each.

Patients with externalized electrodes are expected to spend one hour a day for 2 days during their stay in the hospital or will be tested intraoperatively. We use computer-based mental tasks to distract patients from their pain, decreasing their pain perception. We record their brain, spinal or DRG electrophysiological signals - local field potentials - to analyse what happens to their nervous system when pain decreases. We will also use electrical, thermal and pressure/ pin prick stimulation on patients' limbs, producing graded painful feeling, and record and analyse their signals during the time to see what kind of signals are related to pain.

A control cohort of healthy age-matched subjects that have not experienced chronic pain will be recruited as a comparator group to observe the normal cerebral signature during unaffected by chronic pain.

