## Questions that each state of the experiment could address

### ***Resting state***

1. Brain signals (MEG/EEG/LFPs) recorded during rest sections of the task: the baseline of targets' local field potentials and patients' pain scale.
2. Signals recorded during easy task sections: the response of the targets to the endogenous pain modulation (compared with baseline signals).
3. Signals recorded during difficult task sections: the response of the targets to the endogenous pain modulation (compared with baseline signals)
4. The change of targets' brain signals with different degrees of pain modulation (easy versus difficult task)

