### ***Pain stimulation state***

1. Brain signals recorded during rest sections of the mental task: pain signatures of the targets induced by painful stimulus
2. Brain signals recorded during easy and difficult sections of the mental task: we can investigate how endogenous pain modulation affects the pain signatures induced by painful stimulus

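### State 4 has no non-painful stimulus, so its rest-section signal cannot by itself be attributed to pain

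*Combined protocol and SAP*

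**What the plan says.** The section State 4 – pain stimulation state has patients do the distraction task with the stimulator off and states the purpose of the added stimulus: "We will use peripheral stimulation to induce pain when they are doing the task". It may be heat, "an electrical stimulus, or a mechanical stimulus, just above the pre-measured pain threshold". No lower level is listed there, in States 1 to 3, or in the table of states by task.

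The section Pain stimulation state says what the recordings are for. Item 1 reads: "Brain signals recorded during rest sections of the mental task: pain signatures of the targets induced by painful stimulus". Item 2 turns to the easy and difficult sections: "we can investigate how endogenous pain modulation affects the pain signatures induced by painful stimulus". Neither item names a comparator. The only stated baseline is in the section Resting state, where the State 1 rest sections give "the baseline of targets' local field potentials and patients' pain scale".

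Three other places bear on the point:

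- Summary of Study Design plans further limb stimulation, "producing graded painful feeling, and record and analyse their signals during the time to see what kind of signals are related to pain".
- Inclusion Criteria for patients cover DBS of the ACC, the PAG and the sensory thalamus (VPL or VPM). Background and Rationale acknowledges the thalamus's traditional role as a relay.
- Analysis of Endpoints speaks of testing spectral power but does not say which states are compared.

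**The concern.** Going from State 1 rest to State 4 rest changes two things at once: the patient has more pain, and a limb is being heated, shocked or pressed. A target that responds to any somatosensory input will show a difference whether or not the input hurts. VPL and VPM are the targets where such a response is most to be expected, on the protocol's own description of the thalamus. Item 1 of Pain stimulation state still names the result as "pain signatures of the targets induced by painful stimulus", and the Interventions section presents painful stimulation as a means of learning the neural signature of pain. If that label is carried into the report, an ordinary sensory response could be published as evidence of a pain signature. Recruiting more patients would make the error more likely, because the test gains power to detect the sensory response.

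**Working it through.** **1. What each state varies** (sections State 1 to State 4; Distraction mental task for the section counts)

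| State | Stimulator | Peripheral test stimulus | Rest sections per run |
|---|---|---|---|
| 1 Resting | off | none described | 5 |
| 2 Therapeutic stimulation | on | none described | 5 |
| 3 Medication | off | none described | 5 |
| 4 Pain stimulation | off | painful only | 5 |

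Rest sections with a non-painful stimulus: 0 in every state. The State 4 section does not say whether usual drugs are withheld. I assume they are, as in State 1.

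**2. What the contrasts identify.** Let S be the response to somatosensory input and P the pain-specific response.

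- State 4 rest minus State 1 rest = S + P. No planned LFP condition gives S alone.
- Rest, easy and difficult sections within State 4: the stimulus continues while distraction changes, so a fixed S cancels and a change in P remains. However, rest sections ask patients to attend to their pain, while the task sections add visual search and key presses. Attention, visual input and motor output therefore change too. Subtracting the same contrast in State 1 removes additive task effects, but not an attention effect on S.
- Graded stimulation: every level is painful, so S and P rise together.
- States 1 to 3: pain varies with no test stimulus, so S from a test stimulus is absent. This shows whether a signal tracks pain in general, but does not split the State 4 response.

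**3. Illustration of size.** The plan gives no alpha, effect size, SD or power, and its figure of about 50 participants comes from annual operation numbers. There is no planned calculation to reproduce, and the size of the LFP subset is not stated. All inputs here are assumed: P = 0, two-sided alpha 0.05, and a paired t-test with standardised mean difference d.

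Probability of significance = 1 − F(c; n−1, d√n) + F(−c; n−1, d√n), where F is the noncentral t distribution function and c is the 97.5% point of t on n−1 degrees of freedom.

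| Residual sensory effect d | n = 10 | n = 20 | n = 50 |
|---|---|---|---|
| 0.3 (no-stimulus baseline) | 0.136 | 0.247 | 0.548 |
| 0.5 (no-stimulus baseline) | 0.293 | 0.565 | 0.934 |
| 0.8 (no-stimulus baseline) | 0.616 | 0.924 | 1.000 |
| 0.1 (imperfectly matched non-painful stimulus) | 0.059 | 0.071 | 0.107 |
| 0 (perfectly matched non-painful stimulus) | 0.050 | 0.050 | 0.050 |

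**4. Time for an added condition.** A run is 15 sections × about 1 minute = about 15 minutes. Five more sections make State 4 about 20 minutes. Four states over two days is two runs a day, so the longer day has 15 + 20 = 35 minutes of task against the one hour in Summary of Study Design. That leaves 60 − 35 = 25 minutes for VAS scoring, set-up, state changes and the graded stimulation, none of which the protocol times. The cognitive subtasks (up to 6 × 5 = 30 minutes) are not placed in the schedule. If they share the hour, 35 + 30 = 65 minutes exceeds it. Without the change the sum is already 30 + 30 = 60.

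**The case against.** The strongest reply is that State 4 does not stand alone. The Synopsis defines the primary endpoint through endogenous modulation and DBS, and painful stimulation is not in it. Rationales behind this protocol ties a signature to the VAS and to change under modulation, with painful stimulation as one means among several. VAS is scored after every section in every state. The State 4 distraction sections also allow pain to vary while the stimulus continues. All of this stands, and it rules out several stronger readings that a reader might infer:

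- *That State 4 is the decisive test of the primary objective.* The primary endpoint does not give it that role.
- *That the planned data say nothing about how much of the effect is sensory, or that the VAS correlation shares the whole problem.* The distraction sections and States 1 to 3 carry information, though indirect.
- *That sensory relay will certainly be reported as pain.* No contrast is written down. State 4 minus State 1 is inferred from the stated baseline and from item 1.
- *That hypothesis 2 is undermined.* It holds "that the thalamus can also affect the PAG to modulate pain, rather than being merely a relay centre", which concerns interaction between targets, not the size of one target's evoked response.

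What the reply does not do is justify the label in item 1. Item 2 asks how distraction alters the signature, so it takes item 1 as given. QST includes non-painful modalities, but is described alongside MEG/EEG and not within the LFP states. The Interventions section mentions selective activation of A-delta and C fibres, which might reduce tactile input. It gives no method, and a response to any salient stimulus would remain.

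A below-threshold comparator is also open to criticism, because intensity still differs between the two levels. That is correct: the comparator shrinks the sensory difference without removing it.

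**Conclusion.** The point holds as a limit on interpretation. The State 4 rest-section signal, judged against State 1 rest, is a mixture of sensory and pain responses, and the plan should not call it a pain signature on that evidence alone. The doubt is strongest for VPL and VPM.

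The documents fix no size. Under the assumed inputs, a purely sensory response reaches significance against no stimulus in 14% to almost 100% of studies (d 0.3 to 0.8, n 10 to 50). Against a non-painful stimulus the rate is 5% with perfect matching and 6% to 11% with a residual mismatch of d = 0.1. These figures show the direction and possible scale; they do not predict this study's error rate. The conclusion rests on State 1 rest being the intended comparator, since no other is stated, and on State 4 being off medication like State 1.

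**What to change.** (a) Reword item 1 of Pain stimulation state along these lines: *State 4 rest sections compared with State 1 rest sections give the combined response to peripheral stimulation and pain. A signal is called a pain signature only if it also tracks VAS across rest, easy and difficult sections while the stimulus continues, and in States 1 to 3.* Write the same contrasts into Analysis of Endpoints. This costs only wording and uses data already planned.

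(b) Preferably, also add to State 4 about five one-minute rest sections with the same modality, site and timing but below the pre-measured pain threshold, mixed at random with the above-threshold sections and each followed by the usual VAS. Define the evoked-pain contrast as above minus below threshold within State 4. The equipment and the threshold measurement are already in the plan.

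The costs of (b) are about 5 more minutes plus VAS time in one run, and a small remaining intensity difference between the two levels, which the report must acknowledge. Before adopting it, time a full session, including set-up and graded stimulation, against the one hour a day, and state where the cognitive subtasks fall. If the session does not fit, (a) alone removes the unsupported label.
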